#### 10.7.2. Definition of Medical Device SAE, SADE and USADE

#### A Medical Device SAE is an any serious adverse event that:

- Led to death
- Led to serious deterioration in the health of the participant, that either resulted in:
  - o A life-threatening illness or injury
    - The term *life-threatening* in the definition of *serious* refers to an event in which the participant was at risk of death at the time of the event. It does not refer to an event which hypothetically might have caused death if it were more severe.
  - A permanent impairment of a body structure or a body function
  - Inpatient or prolonged hospitalization; planned hospitalization for a pre-existing condition, or a procedure required by the protocol without serious deterioration in health is not considered an SAE
  - Medical or surgical intervention to prevent life-threatening illness or injury or permanent impairment to a body structure or a body function
  - o Chronic disease (MDR 2017/745)
- Led to fetal distress, fetal death, or a congenital abnormality or birth defect

#### **SADE** definition

 A SADE is defined as an adverse device effect that has resulted in any of the consequences characteristic of an SAE.  Includes any device deficiency that might have led to an SAE if appropriate action had not been taken, intervention had not occurred, or circumstances had been less fortunate.

#### Unanticipated SADE (USADE) definition

An USADE (also identified as UADE in US Regulations 21 CFR 813.3), is defined as
a serious adverse device effect that by its nature, incidence, severity, or outcome has
not been identified in the current version of the risk analysis report (see Section 2.3).

#### 10.7.3. Recording and Follow-Up of AE and/or SAE

#### AE, SAE, and Device Deficiency Recording

- When an AE/SAE occurs, it is the responsibility of the investigator to review all
  documentation (e.g., hospital progress notes, laboratory reports, and diagnostics
  reports) related to the event.
- The investigator will then record all relevant AE/SAE information in the participant's records, in accordance with the investigator's normal clinical practice and on the appropriate form.
- It is **not** acceptable for the investigator to send photocopies of the participant's records to the sponsor in lieu of completion of the AE/SAE form.
- There may be instances when copies of medical records for certain cases are requested by the sponsor. In this case, all participant identifiers, with the exception of the participant number, will be redacted on the copies of the medical records before submission to the sponsor.
- The investigator will attempt to establish a diagnosis of the event based on signs, symptoms, and/or other clinical information. Whenever possible, the diagnosis (not the individual signs/symptoms) will be documented as the AE/SAE.

#### Assessment of Intensity

The investigator will make an assessment of intensity for each AE/SAE reported during the study and assign it to one of the following categories:

- Mild: An event that is easily tolerated by the participant, causing minimal discomfort and not interfering with everyday activities.
- Moderate: An event that causes sufficient discomfort and interferes with normal everyday activities.
- Severe: An event that prevents normal everyday activities.
  - An AE that is assessed as severe should not be confused with an SAE. Severe is a
    category used for rating the intensity of an event; both AEs and SAEs can be assessed
    as severe.

 An event is defined as serious when it meets at least one of the predefined outcomes as described in the definition of an SAE, not when it is rated as severe.

#### **Assessment of Causality**

- The investigator is obligated to assess the relationship between study intervention and each occurrence of each AE/SAE.
- A reasonable possibility of a relationship conveys that there are facts, evidence, and/or
  arguments to suggest a causal relationship, rather than a relationship, cannot be ruled
  out.
- The investigator will use clinical judgment to determine the relationship.
- Alternative causes, such as underlying disease(s), concomitant therapy, and other risk factors, as well as the temporal relationship of the event to study intervention administration will be considered and investigated.
- The investigator will also consult the Investigator's Brochure (IB) in his/her assessment.
- For each AE/SAE/device deficiency, the investigator must document in the medical notes that he/she has reviewed the AE/SAE/device deficiency and has provided an assessment of causality.
- There may be situations in which an SAE has occurred and the investigator has
  minimal information to include in the initial report to the sponsor. However, it is very
  important that the investigator always make an assessment of causality for every event
  before the initial transmission of the SAE data to the sponsor.
- The investigator may change his/her opinion of causality in light of follow-up information and send an SAE follow-up report with the updated causality assessment.
- The causality assessment is one of the criteria used when determining regulatory reporting requirements.

#### Follow-up of Device AE/SAE

- The investigator is obligated to perform or arrange for the conduct of supplemental
  measurements and/or evaluations as medically indicated or as requested by the sponsor
  to elucidate the nature and/or causality of the AE/SAE/device deficiency as fully as
  possible. This may include additional laboratory tests or investigations,
  histopathological examinations, or consultation with other health care professionals.
- If a participant dies during participation in the study or during a recognized follow-up
  period, the investigator will provide the sponsor with a copy of any postmortem
  findings including histopathology.
- New or updated information will be recorded in the originally completed form.

 The investigator will submit any updated SAE data to the sponsor within 24 hours of receipt of the information.

#### 10.7.4. Reporting of SADEs

#### **SADE Reporting**

NOTE: There are additional reporting obligations for medical device deficiencies that are potentially related to SAEs that must fulfil the legal responsibility to notify appropriate regulatory authorities and other entities about certain safety information relating to medical devices being used in clinical studies.

- Any device deficiency that is associated with an SAE must be reported to the sponsor within 24 hours after the investigator determines that the event meets the definition of a device deficiency.
- The sponsor will review all device deficiencies and determine and document in writing
  whether they could have led to an SAE. These device deficiencies will be reported to
  the regulatory authorities and IRBs/IECs as required by national regulations.
- Contacts for SAE reporting can be found in Site Training Materials and Study Contact Information.

## 10.8. Appendix 8: Country-specific Requirements

Not applicable.

## 10.9. Appendix 9: Abbreviations and Definitions

| Abbreviation | Definition   |
|--------------|--|
| 21 CFR       | Code of Federal Regulations, Title 21  |
| 21 CFR 50    | Code of Federal Regulations, Title 21, Part 50, Protection of Human Subjects |
| ADE(s)       | adverse device effect(s)   |
| AE(s)        | adverse event(s)   |
| ANCOVA       | Analysis of Covariance   |
| App          | Application (software)   |
| AST          | aspartate aminotransferase   |
| BUN          | blood area nitrogen  |

| CBT     | cognitive behavioral therapy   |  |
|---------|--|--|
| CGRP    | calcitonin gene-related peptide  |  |
|         |  |  |
| CIOMS   | Council for International Organizations of Medical Sciences, International Ethical Guidelines  |  |
| CMP     | Clinical Monitoring Plan   |  |
| CRF     | case report form   |  |
| CRPS    | complex regional pain syndrome   |  |
| CT-132  | A novel prescription digital therapeutic that is being developed by Click Therapeutics that delivers an interactive, software-based intervention for prevention of migraine. |  |
| DAS     | Defeatist Beliefs Subscale of the Dysfunctional Attitudes Scale  |  |
| DRE(s)  | disease-related event(s)   |  |
| DSM-V   | Diagnostic and Statistical Manual of Mental Disorders, Fifth Edition   |  |
| DTx     | digital therapeutic  |  |
| eCRF    | electronic case report form  |  |
| EDC     | electronic data collection   |  |
| ET      | early termination  |  |
|         |  |  |
| GCP     | Good Clinical Practice Guidelines  |  |
| hCG     | human chorionic gonadotropin   |  |
| HFEM    | High Frequency Episodic Migraine   |  |
| HIPAA   | Health Insurance Portability and Accountability Act  |  |
| IB      | Investigator's Brochure  |  |
| ICD-10  | International Classification of Diseases, Tenth Revision   |  |
| ICF     | informed consent form  |  |
| ICH     | International Council for Harmonisation of Technical Requirements for Registration of Pharmaceuticals for Human Use  |  |
| ICH GCP | International Council for Harmonisation of Technical Requirements for Registration of Pharmaceuticals for Human Use, Good Clinical Practice Guidelines                       |  |
| ID-CM   | Identify Chronic Migraine  |  |

| IDC    | investigational device complaint                |
|--------|---|
| IDFU   | Investigational Directions for Use              |
| IEC(s) | Independent Ethics Committee(s)                 |
| IMP    | investigational medicinal product               |
| INR    | international normalized ratio                  |
| iOS    | iPhone operating system                         |
| IRB(s) | Institutional Review Board(s)                   |
| ITT    | intent-to-treat                                 |
| LFEM   | Low Frequency Episodic Migraine                 |
| MDR    | medical device regulation                       |
| MedDRA | Medical Dictionary for Regulatory Activities    |
| MHD    | monthly headache day(s)                         |
| MIDAS  | Migraine Disability Assessment                  |
| MIDI   | Migraine Disability Index                       |
| mITT   | modified intent-to-treat                        |
| MMD    | monthly migraine day(s)                         |
| MMRM   | Mixed Models Repeated Measures                  |
| MSQ    | Migraine-Specific Quality-of-Life Questionnaire |
| NIMP   | non-investigational medicinal product           |
| NSAID  | nonsteroidal anti-inflammatory drug             |
| PDT    | prescription digital therapeutic                |
| PGI-C  | Patient Global Impression of Change             |
|        |   |
| PMR    | progressive muscle relaxation                   |
| PP     | per protocol                                    |
| QTLs   | Quality Tolerance Limits                        |
| SADE   | serious adverse device effect                   |
| SAE(s) | serious adverse event(s)                        |
| SaMD   | software-as-a-medical device                    |
| SAP    | Statistical Analysis Plan                       |

| SDS        | Sheehan Disability Scale   |
|------------|--|
| SMS        | short message service (the most common form of text messages)                    |
| SoA        | Schedule of Assessments and Activities   |
| SoC        | standard of care   |
| TOC        | table of contents  |
| ULN        | upper limit of normal  |
| USADE/UADE | unanticipated serious adverse device effect/ unanticipated adverse device effect |
| VLFEM      | Very Low Frequency Episodic Migraine   |
| WHODAS 2.0 | WHO Disability Assessment Schedule 2.0   |
| YLD        | years lived with disability  |

## 10.10. Appendix 10: Protocol History

| DOCUMENT HISTORY     |             |  |
|----------------------|-------------|--|
| Document             | Date        |  |
| Protocol Amendment 3 | 08 May 2024 |  |
|                      |             |  |
|                      |             |  |
|                      |             |  |

CT-132	A novel prescription digital therapeutic that is being developed by Click Therapeutics that delivers an interactive, software-based intervention for prevention of migraine.
eDiary	electronic Diary
EDC	Electronic Data Collection
HFEM	High Frequency Episodic Migraine
ICF	Informed Consent Form
ITT	Intent-to-Treat
IWRS	Interactive Web Response System
LFEM	Low Frequency Episodic Migraine
LSM	Least Squares Means
MAR	Missing at Random
MedDRA	Medical Dictionary for Regulatory Activities
MHD(s)	Monthly Headache Day(s)
MIDAS	Migraine Disability Assessment
MI	Multiple Imputation
mITT	Modified Intent-to-Treat
MMD(s)	Monthly Migraine Day(s)
MNAR	Missing Not at Random
MSQ	Migraine-Specific Quality-of-Life Questionnaire
PGI-C	Patient Global Impression of Change
PMM	Predictive Mean Matching
PP	Per Protocol
PT	Preferred Term
QoL	Quality of Life
SAE	Serious Adverse Event
SAP	Statistical Analysis Plan
SD	Standard Deviation
SE	Standard Error
SOC	System Organ Class
TEAE	Treatment Emergent Adverse Event
VLFEM	Very Low Frequency Episodic Migraine

1. INTRODUCTION

This Statistical Analysis Plan (SAP) describes the planned analysis for Click Therapeutics study CT-132-R-001, "A Randomized Double-blind, Digital-Controlled, Parallel-Group, Virtual Study to Evaluate the Effectiveness and Safety of a Digital Therapeutic (CT-132) as Adjunctive Therapy in Late Adolescents and Adults for the Prevention of Episodic Migraine". This SAP should be read together with the protocol for full details on the study.

The SAP is intended to agree with the protocol with regard to statistical aspects that were specified in the protocol. However, the SAP may contain additional details for analyses that were defined in the protocol, and may provide details on statistical aspects that were not described in the protocol. In case of disagreement between the SAP and the protocol, the SAP prevails. Differences will be described in the statistical report and at the end of this document.

2. STUDY OBJECTIVES AND ESTIMANDS

2.1. Study Objectives

The study objectives are to evaluate the effectiveness and safety of CT-132 in reducing the number of monthly migraine days (MMDs), compared with a Digital Control, among late adolescents and adults with migraine.

The study endpoints to support these objectives are listed in Section 3.

2.2. Primary Estimand

The primary estimand will be the effect of the digital therapeutic (CT-132) on number of MMDs regardless of use of prohibited medications, adherence to treatment or early termination for any reason.

This estimand considers the following intercurrent events:

- Use of prohibited medications
- Lack of adherence
- Early discontinuation due to any reason

Since participants may use their prescribed medication to treat episodic migraine (including changes in medication or dosage) as needed while continuing to use the Study App, and since the study population is defined as participants diagnosed with migraine and taking first- and second-line preventive medications, the use of these medications is not considered an intercurrent event.

Attributes of the primary estimand:

- The **treatment condition** of interest is CT-132 compared to a digital control, both alongside prescribed medications, to treat episodic migraine
- The **population** is late adolescents and adults with episodic migraine who fulfill all of the inclusion criteria and none of the exclusion criteria for the study
- The **endpoint** to be considered is the change from baseline (28-day run-in period) in MMDs to week 12 (previous 28 days, Weeks 9-12)
- The **population-level summary** is the least squares mean (LSM) difference between CT-132 and the digital control

Strategies for Addressing Intercurrent Events in Primary Estimand

- Use of prohibited medications: In case of use of prohibited medications, participants will be discontinued from the study and the Study App will be disabled for them. Data accumulated until the Study App is disabled will be included in the analysis. This approach complies with the treatment policy strategy.
- Lack of adherence: The treatment effect of CT-132 will be estimated regardless of lack of adherence to lessons and activity. This approach complies with the treatment policy strategy.

• Early discontinuation due to any reason: The treatment effect of interest is regardless of early discontinuation of treatment which complies with the treatment policy strategy. For that reason, data that does not exist after early discontinuation will be considered as missing data, and will be imputed as described in Section 6.3.

3. STUDY ENDPOINTS

Unless otherwise specified, effectiveness endpoints will be evaluated as a comparison between the CT-132 treatment group and the digital control group.

3.1. Primary Effectiveness Endpoints

Change in the number of MMDs from baseline (28-day run-in period) to Week 12 (previous 28 days, Week 9 through Week12).

3.2. Secondary Effectiveness Endpoints

- Proportion of participants who have at least a 50% reduction from baseline (28-day run-in period) in the number of MMDs to Week 12 (previous 28 days, Week 9 through Week 12).
- Change from baseline (28-day run-in period) in the number of MMDs recorded over the previous 28 days at Week 4 and at Week 8.
- Change from baseline (28-day run-in period) in the mean number of MMDs over 12 weeks.
- Change in the number of headaches with at least moderate severity from baseline (28-day runin period) to Week 12 (previous 28 days, Week 9 through Week 12).
- Change from baseline (28-day run-in period) in the Migraine-Specific Quality-of-Life Questionnaire v2.1 (MSQ) total score over the previous 28 days at Week 4, Week 8, and Week 12.
- Change from baseline (28-day run-in period) in the Migraine Disability Assessment (MIDAS) to Week 12 (previous 28 days, Week 9 through Week 12).
- Change from baseline (28-day run-in period) to Week 12 (previous 28 days, Week 9 through Week 12) in the number of migraines with use of an acute medication.
- Change in the number of MHDs from baseline (28-day run-in period) to Week 12 (previous 28 days, Week 9 through Week 12).

3.3. Exploratory Endpoints

- Monthly headache days (MHDs):
 - Change from baseline (28-day run-in period) in the number of MHDs recorded over the previous 28 days at Week 4 and at Week 8.

- o Proportion of participants who have at least a 50% reduction from baseline (28-day run-in period) in the number of MHDs at Week 12 (previous 28 days, Week 9 through Week 12).
- Change from baseline (28-day run-in period) in the mean number of MHDs over 12 weeks. .
- Patient Global Impression of Change (PGI-C) score at Week 12.
- Shift from High Frequency Episodic Migraine (HFEM) at baseline (28-day run-in period) to Very Low Frequency Episodic Migraine (VLFEM) or Low Frequency Episodic Migraine (LFEM) at Week 12 (previous 28 days, Week 9 through Week 12).

3.4. Safety Endpoints

- Frequency and severity of Adverse Events (AE), serious AEs (SAE), and discontinuation from the study due to AEs.
- Frequency and severity of AEs related to the worsening of migraine.

4. STUDY DESIGN

4.1. General Design

This is a randomized, double-blind, digital-controlled, parallel-group, virtual study to assess the effectiveness and safety of CT-132 in late adolescents and adults for the prevention of migraine in comparison to a digital control. Eligible participants must report having four or more migraine days per month in the three months prior to the Screening Visit. All participants will complete an identical, pre-randomization onboarding experience, which includes verifying participant understanding of and interest in the study, and a run-in period to capture baseline MMDs within the Study App. During the run-in period and intervention period, these participants will continue to take their healthcare provider-prescribed acute and first- and second-line preventive medications for the treatment of migraine, while continuing to use the Study App to report headache and symptoms and medications. This daily reporting is referred to below as eDiary use. Upon successful completion of the onboarding experience, run-in period, and confirmation of participant interest and eligibility, the participant will be randomized at the baseline study visit. The duration of participation will be approximately 19 weeks, including an up-to-14-day screening period, a 28-day run-in period, a 12-week double-blind intervention period, and an up-to-7-day follow-up period for safety assessments.

The activities and assessments during the 2-week screening period, the 4-week run-in period, the 12-week double-blind intervention period, and the 1-week follow-up period will be completed according to the Schedule of Activities and Assessments (Protocol Section 1.2). Trial staff will implement procedures remotely. Participants will be assessed based on validated standard clinician-rated and participant-rated outcome scales for migraine at screening, the intervention period, and the follow-up period. Participants will also be evaluated for safety throughout the duration of the trial.

4.2. Sample Size and Power Considerations

Assuming a difference of 1.6 in the mean MMDs between the two arms, and a common standard deviation (SD) of 5.8, 474 participants are required for the study (237 per arm) to ensure 85% power and using a two-sided alpha of 5%. Sample size was calculated using a two-sample *t*-test assuming equal variance. Assuming 15% drop out, at least 558 participants will be randomized in a 1:1 ratio to CT-132 or digital control.

4.3. Randomization and Blinding

All participants will be centrally assigned to randomized study intervention using an Interactive Web Response System (IWRS). The IWRS will be integrated into the electronic data collection (EDC) system. Study team(s) will refer to the randomization information in the EDC system.

Participants will be randomly assigned in a 1:1 ratio to receive either CT-132 or the digital control as study intervention through the Study App. Investigators and designated personnel will remain blinded to each participant's assigned study intervention throughout the course of the study.

Study participants will be blinded to the effectiveness hypothesis of the study. Both treatment arms will be presented to the participant as possible treatments for migraine. No references to CT-132

or digital control will be made to the participant. This approach limits the risk of participant unblinding to treatment assignment and expected effectiveness.

4.4. Planned Timing of Analysis

Final analysis will be performed after all participants have completed the study, the SAP is finalized, and database is locked and study is unblinded.

5. ANALYSIS SETS

5.1. Consented Analysis Set

[figure not shown]
The Consented Analysis set includes all participants who signed the Informed Consent Form (ICF).

5.2. Enrolled Analysis Set

The Enrolled Analysis set includes all participants who signed the ICF and completed the run-in period.

5.3. Intention-to-Treat (ITT) Analysis set

The ITT set includes all enrolled participants who were randomized, based on the assigned intervention in the randomization and recorded in the database, regardless of treatment by Study App intervention. This will be the main analysis set for all effectiveness analyses.

5.6. Safety Analysis set

The safety analysis set includes all randomized participants who are exposed to the study intervention (completed at least one task). Participants will be analyzed according to the intervention they received. This analysis set will be used for all safety analyses.

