# 2.2. Background

# 2.2.1. Migraine

#### 2.2.2. CT-132

#### 2.3. Benefit/Risk Assessment

#### 2.3.1. Risk Assessment

No AEs are anticipated specific to CT-132, due to its software-only nature. The primary potential risk to the participant that could lead to AEs is the temporary worsening of migraine symptoms. These and other potential risks may be considered minimal, and no greater than those associated with SoC therapies for the treatment of migraine.

Participants may experience some AEs due to their underlying condition or with the use of adjunctive treatment. The risk profile of SoC used in clinical practice is well understood and is detailed in their respective package inserts.

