## 9.3. Analysis Sets

For the purposes of analysis, the following analysis sets are defined:

| Analysis Set          | Description  |
|-----------------------|--|
| Consented             | All participants who signed the ICF.   |
| Enrolled              | All participants who signed the ICF and completed the run-in period.   |
| Intent-To-Treat (ITT) | The ITT set includes all enrolled participants who were randomized, based on the assigned intervention in the randomization and recorded in the database, regardless of treatment by Study App intervention.  This will be the main analysis set for all effectiveness analysis. |

| Modified Intent-to-Treat (mITT) |  |
|---------------------------------|--|
| Per Protocol (PP)               |  |
| Safety                          | All randomized participants who were exposed to study intervention (completed at least one task). Participants will be analyzed according to the intervention they received. This analysis set will be used for all safety analyses. |

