7.3. Medical History and Medications

The medical history and medication analysis will be performed using the ITT analysis set.

Medical history will be summarized and presented by treatment group.

The proportion of participants who received previous therapy will be summarized by WHOdrug preferred term and presented by treatment group. A separate summary will be presented for migraine medications taken prior to the study.

The proportion of patients who report concomitant medications during study treatment will be summarized by WHOdrug preferred term and presented by treatment group regardless of whether the medication was taken prior to baseline.

Previous therapy is defined as medication with end date earlier than the baseline date (study app activation).

Concomitant medication is defined as medication with an end date on or later than the baseline date (study app activation) or missing end date.

The proportion of participants who use acute migraine medication and preventive migraine medication will be summarized, separately, by WHOdrug preferred term and presented by treatment group.

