7.6. Exposure

Exposure to study intervention, in days, will be calculated for each participant as number of days from first day of treatment until last day of treatment + 1. First day of treatment is defined as the first date with adherence to task and last day of treatment is defined as the last date of adherent to task.

Exposure will be summarized using descriptive statistics by treatment group.

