9. SAFETY ANALYSIS

All safety analyses will be conducted on the safety analysis set and will be descriptive.

AE will be recorded from date of signing the ICF and onwards. All AEs will be coded by system organ class (SOC) and preferred term (PT) using Medical Dictionary for Regulatory Activities (MedDRA) version 25.1.

Summaries will present non-treatment emergent AEs (AEs started before first day of treatment) and treatment-emergent AEs (TEAE; AEs started after first day of treatment) separately.

In an overview table, the number and percentage of participants who experienced a TEAE, non-TEAE, serious TEAE, treatment related TEAE, died due to an AE, or discontinued from study treatment due to a TEAE will be summarized by treatment.

The percentages of participants with TEAEs will be summarized by treatment using MedDRA preferred term nested within system organ class (SOC). Events will be ordered by decreasing frequency within SOC, and SOC with be ordered by decreasing frequency.

Similar summary will be presented for non-TEAE, serious TEAE, treatment related TEAE and TEAE related to worsening of migraine.

AEs with missing start date will be considered as a TEAE.

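### Safety-set entry and treatment-emergent status begin at the first completed task rather than at app activation, which leaves a small, avoidable gap in the safety tables

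*SAP*

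**What the plan says.** Both documents tie exposure to task completion. Protocol 9.3: "All randomized participants who were exposed to study intervention (completed at least one task". SAP 5.6 repeats the rule: "The safety analysis set includes all randomized participants who are exposed to the study intervention (completed at least one task". SAP 9 applies the set throughout: "All safety analyses will be conducted on the safety analysis set and will be descriptive".

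The start of treatment has more than one anchor:

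- SAP 7.6 (Exposure): "First day of treatment is defined as the first date with adherence to task".
- SAP 7.3 (medications): "Previous therapy is defined as medication with end date earlier than the baseline date (study app activation". Here the anchor is activation.
- SAP 6.1 counts study days from the baseline visit and treats Day 1 onward as the treatment period.
- Protocol 4.1.3 has randomization at the baseline visit unlock the assigned experience in the app.

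SAP 9 splits AEs at the first day of treatment: "Summaries will present non-treatment emergent AEs (AEs started before first day of treatment", with those starting after that day treated as treatment-emergent. Protocol 8.4.1 places the cut at or after first study treatment, without saying which date that is.

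Protocol 2.3.1 names the main safety concern: "The primary potential risk to the participant that could lead to AEs is the temporary worsening of migraine symptoms".

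**The concern.** Contact with the assigned intervention is possible from the moment the app is unlocked. Under the current wording, what a participant does after that moment decides two things: whether the participant enters the safety set at all, and whether an AE counts as treatment-emergent. A safety population is better defined by something fixed before any effect of the intervention can appear.

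At stake is the completeness of the descriptive safety tables, above all those for the named safety endpoints: AEs related to worsening of migraine, and discontinuation due to AEs. No hypothesis test or success criterion depends on the safety set.

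**Working it through.** **1. Who is outside the safety set.** Entry requires randomization and at least one completed task (Protocol 9.3, SAP 5.6). A participant who opens the unlocked app, starts a task, stops, and never completes any task later is randomized but not in the set, and so is in no analysis run on it. Someone who abandons one session and completes a task on another day stays in.

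**2. What still captures that participant.** AEs are collected from consent to the follow-up visit whatever the app use (Protocol 8.4.1). Disposition runs on the consented set and gives discontinuations by reason (SAP 7.1), so an exit because of an AE is counted there. Disposition does not give the AE term, severity or relatedness. The content of the SAP listings is not in the public text, so absence from listings cannot be asserted.

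**3. How an early AE is classed for participants in the set.** Take activation at baseline (Day 0 in SAP 6.1), first adherence to a task on Day 5, and an AE starting on Day 3.

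| Rule | Status of Day 3 |
|---|---|
| SAP 6.1 | within the treatment period |
| SAP 7.3 | after activation; a drug stopped that day is concomitant, not previous |
| SAP 7.6 read with SAP 9 | before first day of treatment, so the AE is a non-TEAE |
| Protocol 8.4.1 | depends on what first study treatment means |

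SAP 9 does not cross-refer to 7.6, but 7.6 is the only place in the public text where the first day of treatment is defined.

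**4. What a non-TEAE loses.** SAP 9 gives non-TEAEs a line in the overview table and their own summary by system organ class and preferred term, together with events dating back to consent. The serious, treatment-related and migraine-worsening summaries, and the overview line for stopping treatment because of an AE, are specified for TEAEs. The Day 3 event is therefore tabulated, but not in those summaries. An AE with a missing start date counts as a TEAE.

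**5. Possible size.** The only relevant planned figure is the number randomized, which reproduces: 474 / (1 − 0.15) = 557.6, so 558. The documents do not say how many will activate the app without completing a task. For an assumed share f, the number outside the set is 558 × f:

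| Assumed f | Outside the set | Remaining |
|---|---|---|
| 0% | 0 | 558 |
| 1% | 6 | 552 |
| 2% | 11 | 547 |
| 5% | 28 | 530 |
| 10% | 56 | 502 |

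**6. Cost of widening the set.** If the added participants had no AEs, every AE percentage would be multiplied by remaining / 558: 552/558 = 0.989 at 1%, and 530/558 = 0.950 at 5%. That is a relative reduction of about 1% to 5%.

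**The case against.** The strongest reply is that requiring actual use is the ordinary received-treatment convention, and that unlocking the app with a code is closer to dispensing than to exposure. The protocol and SAP also agree on the set. Participants have passed a 28-day run-in with at least 80% adherence (Protocol synopsis), are given daily tasks, and have an adherence check after 3 inactive calendar days (Schedule of Activities, note f), so never completing a task should be rare. The public text does not define a task: Protocol 6.4 and SAP 7.5 are not shown. If an eDiary entry or short onboarding step qualified, almost nobody would be excluded, and the first adherent date would nearly equal activation.

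Most of this stands as a limit on size. The eDiary reading is less likely, because SAP 2.2 speaks of adherence to lessons and activity and the eDiary is already in use during run-in, but it cannot be ruled out. SAP 7.3 serves a different purpose from AE classification, so the differing anchors are an inconsistency to settle rather than proof of error.

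A reader might infer three stronger things that the documents do not support:

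- **That excluded participants have no safety follow-up, or that early AEs are lost.** AEs are still collected, disposition shows the reasons for leaving, and non-TEAEs are tabulated for participants in the set.
- **That worsening migraine is the event most likely to prevent a first task.** It is the main named risk and the mechanism is plausible, but nothing in the documents shows it. Expected symptoms of the studied disease are not AEs unless more severe than expected (Protocol Appendix 3).
- **That exclusions will differ by arm.** Protocol 6.1.2 describes a comparable experience with similar daily engagement, and no difference in first tasks is shown.

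**Conclusion.** The point holds in a limited form and is minor. As written, the plan makes safety-set membership and treatment-emergent status depend on behaviour after the app is unlocked, and its start-of-treatment date is not the activation or baseline date used in SAP 7.3 and 6.1. Participants who never complete any task are outside all safety-set analyses. AEs between activation and the first adherent date are shown only as non-TEAEs.

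The number affected is unknown and probably small. The range of 6 to 28 people rests on an assumed 1% to 5%, with no support in the documents for either end. The conclusion also assumes that a task means intervention content rather than a diary entry, and that SAP 9 uses the date defined in SAP 7.6. The primary analysis, the sample size and the success criterion are untouched.

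**What to change.** - In Protocol 9.3 and SAP 5.6, define the safety set as all randomized participants whose assigned app was activated. The intervention received is fixed at unlocking, so analysis by intervention received still works.
- In SAP 9, start treatment-emergence at the activation date. SAP 7.6 can keep the first adherent date for duration of exposure.
- While editing SAP 9, reconcile its before/after wording with Protocol 8.4.1. An AE starting on the first day of treatment is now in neither SAP class, while the protocol cut is at or after first treatment.
- Keep completion of at least one task as a secondary safety cut.
- At minimum, if the current set is kept, define a task and tabulate the AEs of randomized participants outside the set by arm.

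The cost is a few changes of wording and one extra cut of the AE tables. No new data are needed, since SAP 7.3 already relies on the activation date. The downside is slight dilution of AE percentages by people who never used the app (about 1% to 5% in relative terms under the assumed shares), which the secondary cut makes visible.
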